10.4 Informed Consent

The informed consent form (ICF) and process must comply with the United States regulations (§ 21 CFR Part 50) as well as country specific national regulations and/or local laws. The ICF will document the study-specific information the Investigator or his/her designee provides to the subject and the subject's agreement to participate.

The Investigator, or designee (designee must be listed on the Delegation of Authority log), **must** explain in terms understandable to the subject the purpose and nature of the study, study procedures, anticipated benefits, potential risks, possible adverse effects, and any discomfort participation in the study may entail. This process must be documented in the subject's source record. Each subject must provide a signed and dated informed consent before any study-related (nonstandard of care) activities are performed (such as screening). The original and any amended signed and dated consent forms must remain in each subject's study file at the study site and be available for verification by study monitors at any time. A copy of each signed consent form must be given to the subject at the time that it is signed by the subject.

11.0 CONTROL AND QUALITY ASSURANCE

11.1 Protected Subject Health Information Authorization

Information on maintaining subject confidentiality in accordance with individual local and national subject privacy regulations must be provided to each subject as part of the informed consent process (refer to [Section 10.4](#)) either as part of the informed consent form or as a separate signed document (for example, in the US, a site-specific Health Insurance Portability and Accountability Act [HIPAA] consent may be used). The Investigator or designee **must** explain to each subject that for the evaluation of study results, the subject's protected health information obtained during the study may be shared with BNI and its designees, regulatory agencies, and IRBs/REBs/IECs. As the study Sponsor, BNI will not use the subject's protected health information or disclose it to a third party without applicable subject authorization. It is the Investigator's or designee's responsibility to obtain written permission to use protected health information from each subject. If a subject withdraws permission to use protected health information, it is the Investigator's responsibility to obtain the withdrawal request in writing from the subject **and** to ensure that no further data will be collected from the subject. Any data collected on the subject before withdrawal will be used in the analysis of study results.

During the review of source documents by the monitors or auditors, the confidentiality of the subject will be respected with strict adherence to professional standards and regulations.

11.2 Study Files and Record Retention

The Investigator **must** keep a record that lists **all** subjects considered for enrollment (including those who did not undergo screening) in the study. For those subjects subsequently excluded from enrollment, the reason(s) for exclusion is to be recorded.

The Investigator/study staff must maintain adequate and accurate records to enable the conduct of the study to be fully documented and the study data to be subsequently verified. Essential documentation includes, but is not limited to, the Investigator's Brochure, signed protocols and amendments, IRB/REB/IEC approval letters (dated), signed FDA Form 1572 and Financial Disclosures, signed ICFs (including subject confidentiality information), drug dispensing and accountability records, shipping records of investigational product and study-related materials, signed (electronically), dated and completed CRFs, and documentation of CRF corrections, SAE forms transmitted to BNI or designee and notification of SAEs and related reports, source documentation, normal laboratory values, decoding procedures for blinded studies, curricula vitae for study staff, and all relevant correspondence and other documents pertaining to the conduct of the study.

All essential documentation will be retained by the Investigator for at least 2 years after the date the last marketing application is approved for the drug for the indication for which it is being investigated and until there are no pending or contemplated marketing applications; or, if no application is to be filed or if the application is not approved for such indication, until 2 years after formal discontinuation of clinical development of the drug.

The Investigator must notify BNI and obtain written approval from BNI before destroying any clinical study documents or images (e.g., scan, radiograph, ECG tracing) at any time. Should an Investigator wish to assign the study records to another party or move them to another location, advance written notice will be given to BNI. BNI will inform the Investigator of the date that study records may be destroyed or returned to BNI.

BNI must be notified in advance of, and BNI must provide express written approval of, any change in the maintenance of the foregoing documents if the Investigator wishes to move study records to another location or assign responsibility for record retention to another party. If the Investigator cannot guarantee the archiving requirements set forth herein at his or her study site for all such documents, special arrangements must be made between the Investigator and BNI to store such documents in sealed containers away from the study site so that they can be returned sealed to the Investigator for audit purposes.

11.3 Case Report Forms and Record Maintenance

Electronic case report forms (eCRFs) will be used to collect the clinical study data and must be completed for each enrolled subject with all required study data accurately recorded such that the information matches the data contained in medical records (e.g., physicians' notes, nurses' notes, clinic charts and other study-specific source documents). Authorized study site personnel (i.e., listed on the Delegation of Authority form) will complete eCRFs designed for this study according to the completion guidelines that will be provided. The Investigator will ensure that the eCRFs are accurate, complete, legible, and completed within 5 days of each subject's visit. At all times, the Investigator has final responsibility for the accuracy and authenticity of all clinical data.

The eCRFs exists within an electronic data capture (EDC) system with controlled access managed by BNI or its authorized representative for this study. Study staff will be appropriately trained in the use of eCRFs and application of electronic signatures before the start of the study and before being given access to the EDC system. Original data and any changes of data will be recorded using the EDC system, with all changes tracked by the system and recorded in an electronic audit trail. The Investigator attests that the information contained in the eCRFs is true by providing electronic signature within the EDC system. After database lock, the Investigator will receive a copy of the subject data (e.g., paper, CD-ROM or other appropriate media) for archiving at the study site.

11.4 Study Monitoring/ Audit Requirements

Representatives of BNI or its designee will monitor this study until completion. Monitoring will be conducted through personal visits with the Investigator and site staff, remote monitoring, as well as any appropriate communications by mail, fax, email, or telephone. The purpose of monitoring is to ensure that the study is conducted in compliance with the protocol, standard operating procedures (SOPs), and other written instructions and regulatory guidelines, and to ensure the quality and integrity of the data. This study is also subject to reviews or audits.

To assure the accuracy of data collected in the CRFs, it is mandatory that the monitor/auditor have access to all original source documents, including all electronic medical records (EMR) at reasonable times and upon reasonable notice. During the review of source documents, every effort will be made to maintain the anonymity and confidentiality of all subjects during this clinical study. However, because of the experimental nature of this treatment, the Investigator agrees to allow the IRB/REB/IEC, representatives of BNI, its designated agents and authorized employees of the appropriate Regulatory Authority to inspect the facilities used in this study and, for purposes of verification, allow direct access to the hospital or clinic records of all subjects enrolled into this study. A statement to this effect will be included in the informed consent and permission form authorizing the use of protected health information.

BNI or its authorized representative may perform an audit at any time during or after completion of this study. All study-related documentation must be made available to the designated auditor. In addition, a representative of the FDA or other Regulatory Agencies may choose to inspect a study site at any time before, during, or after completion of the clinical study. In the event of such an inspection, BNI will be available to assist in the preparation. All pertinent study data should be made available as requested to the Regulatory Authority for verification, audit, or inspection purposes.

11.5 Investigator Responsibilities

A complete list of Investigator responsibilities are outlined in the clinical trial research agreement and the Statement of Investigator FDA Form 1572, both of which are signed by the Investigator before commencement of the study. In summary, the Investigator will conduct the study according to the current protocol; will read and understand the Investigator's Brochure; will obtain IRB/REB/IEC approval to conduct the study; will obtain informed consent from each study participant; will maintain and supply to the Sponsor or designee, auditors and regulatory agencies adequate and accurate records of study activity and drug accountability for study-related monitoring, audits, IRB/REB/IEC reviews and regulatory inspections; will report SAEs to the Sponsor or designee and IRB/ REB/IEC according to the specifics outlined in this protocol; will personally conduct or supervise the study; and will ensure that colleagues participating in the study are informed about their obligations in meeting the above commitments.

11.6 Sponsor Responsibilities

A complete list of the Sponsor responsibilities is outlined in the clinical trial research agreement and in the laws and regulation of the country in which the research is conducted. In summary, the Sponsor will select qualified Investigators, provide them with the information they need to properly conduct the study, ensure adequate monitoring of the study, conduct the study in accordance with the general investigational plan and protocols and promptly inform Investigators, health and regulatory agencies/authorities as appropriate of significant new adverse effects or risks with respect to the drug.

11.7 Financial Disclosure

A separate financial agreement will be made between each Principal Investigator and BNI or its authorized representative before the study drug is delivered.

For this study, each Investigator and Sub-investigator (as designated on the FDA 1572 form) will provide a signed Financial Disclosure Form in accordance with § 21 CFR 54. Each Investigator will notify BNI or its authorized representative of any relevant changes during the conduct of the study and for 1 year after the study has been completed.

11.8 Liability and Clinical Trial Insurance

In the event of a side effect or injury, appropriate medical care as determined by the Investigator/designee will be provided.

If a bodily injury is sustained, resulting directly from the use of the study drug, BNI will reimburse for reasonable physician fees and medical expenses necessary for treatment of only the bodily injury which is not covered by the subject's medical or hospital insurance, provided that the injury is not due to a negligent or wrongful act or omission by the Investigator/study staff. The Informed Consent Form will include a description of this reimbursement policy, incorporating country-specific national regulations and/or local laws. Financial compensation for lost wages, disability or discomfort due to the study is not available.

Clinical trial insurance has been undertaken according to the laws of the countries where the study will be conducted. An insurance certificate will be made available to the participating sites at the time of study initiation upon request.

11.9 Protocol Amendments

BNI will initiate any change to the protocol in a protocol amendment document. The amendment will be submitted to the IRB/REB/IEC together with, if applicable, a revised model informed consent form (ICF). Written documentation of IRB/REB/IEC and required site approval must be received by BNI before the amendment may take effect at each site. Additionally under this circumstance, information on the increased risk and/or change in scope must be provided to subjects already actively participating in the study, and they must read, understand and sign any revised ICF confirming willingness to remain in the trial.

No other significant or consistent change in the study procedures, except to eliminate an immediate hazard, shall be effected without the mutual agreement of the Investigator and BNI.

12.0 PUBLICATION OF STUDY RESULTS

BNI may use the results of this clinical study in registration documents for Regulatory Authorities in the United States or abroad. The results may also be used for papers, abstracts, posters or other material presented at scientific meetings or published in professional journals or as part of an academic thesis by an Investigator. In all cases, to avoid disclosures that could jeopardize proprietary rights and to ensure accuracy of the data, BNI reserves the right to preview all manuscripts and abstracts related to this study, allowing BNI sufficient time to make appropriate comments before submission for publication.

In most cases, the Principal Investigators at the sites with the highest accruals of eligible subjects shall be listed as lead authors on manuscripts and reports of study results. This custom can be adjusted upon mutual agreement of the authors and BNI.

12.1 Study Discontinuation

The Sponsor reserves the right to terminate the study at any time. Should this be necessary, both the Sponsor and the Investigator will arrange discontinuation procedures. In terminating the study, the Sponsor and the Investigator will assure that adequate consideration is given to the protection of the subjects' interests.

14.0 APPENDICES
14.1 Schedule of Events

All Treatment Visits have a ± 3 day window LTFU Visits have a ±14 day window	Screening	Treatment								Long-Term Follow-Up	
	Week	1	3	5	9	13	17	21	25	1 st visit (6 mos after EoT)	Every subsequent 6 mos ^{16*}
	Day -28 – -1								EoT		
Dosing: PROSTVAC-V or placebo¹		X									
Dosing: PROSTVAC-F or placebo¹			X	X	X	X	X	X			
GM-CSF or placebo²		X	X	X	X	X	X	X			
Immune Monitoring**											
Immune/Biomarker Status		X							X	X	
Peripheral Blood RNA		X							X	X	
Tumor CTC (US sites only)		X							X	X	
Immune function (US sites only)		X							X	X	
Procedures											
Informed Consent	X										
Medical History	X										
Prostate Cancer History	X										
Prostate Cancer Treatment Update										X	X
Complete Physical Exam ³	X								X		
Abbreviated Physical Exam ⁴		X	X	X	X	X	X	X		X ¹³	X ¹³
Vital Signs ⁵	X	X	X	X	X	X	X	X	X	X	
Autoimmune Disease Status										X ¹⁴	X ¹⁴
ECOG	X	X	X	X	X	X	X	X	X		
Adverse Events	X	X	X	X	X	X	X	X	X		
Concomitant Medications	X	X	X	X	X	X	X	X	X	X ¹⁵	
ECG	X								X		
Quality of Life Questionnaire***		X							X	X	
Laboratory Assessments											
HLA-A2 typing		X									
PSA and PAP	X	X ⁸		X	X	X	X	X	X	X	
Testosterone	X										
Hematology ⁶	X	X ⁸		X	X	X	X	X	X		
Serum Chemistry ⁷	X	X ⁸		X	X	X	X	X	X		
Cardiac Markers ⁹	X										
HIV, HBsAg, HepC ¹⁰	X										
PT(INR)/PTT	X								X		
C-Reactive Protein	X								X		
Urinalysis	X								X		

14.1 Schedule of Events (Continued)

All Treatment Visits have a ± 3 day window LTFU Visits have a ±14 day window	Screening	Treatment								Long-Term Follow-Up	
	Week	1	3	5	9	13	17	21	25	1 st visit (6 mos after EoT)	Every subsequent 6 mos ^{16*}
Radiology Assessments											
Bone Scan	X ¹¹					X			X	X	
CT Scan with contrast (pelvis and abdomen) ^{****}	X ¹¹					X ¹²			X	X	

* Until 12 months after the projected number of events is realized or death, whichever is first.

** Immune monitoring samples should be collected only after a patient is eligible by all other criteria and prior to the first dose of study drug (US Only).

*** QOLs include: FACT-P, BPI-SF, and EQ-5D-3L to be performed at Week 1 and Week 25 during the Treatment Phase and at Month 6 during the LTFU Phase.

**** For subjects enrolled in Germany, MRI must be used as the primary imaging modality

1. Subject should remain in the clinic for at least 30 minutes following administration of PROSTVAC-V/F/ placebo for observation of adverse reaction.
2. GM-CSF or placebo will be administered the day of vaccination and following 3 consecutive days.
3. A Complete Physical Examination will include, at a minimum, the general appearance of the subject, height (screening only) and weight, and examination of the skin, eyes, ears, nose, throat, lung, heart, abdomen, extremities, musculoskeletal system, genitourinary system, nervous system, and lymphatic system
4. Abbreviated physical examinations will be driven by problems or issues identified during the Treatment Phase and during the LTFU Phase that have changed since Screening
5. Vital signs will include including sitting BP, heart rate, RR, temperature, and weight
6. Hematology: CBC with differential, RBC with indices, platelets
7. Serum chemistry: BUN, creatinine, ALT, AST, alkaline phosphatase, total bilirubin, LDH, sodium potassium, chloride, bicarbonate, calcium and glucose
8. Blood samples do not need to be repeated at Day 1, if screening samples were run within 7 days of the visit
9. Cardiac Markers (CK, CK-MB, Troponins T and I)
10. Virology testing required unless known negative within the previous 2 months
11. Baseline Bone Scan and CT Scan of the abdomen and pelvis (if not performed within 3 months of the start of Screening); for subjects with allergies to contrast agents, MRIs for abdomen and pelvis may be performed. Only in cases where MRI is unavailable may a non-contrast CT be performed.
12. If clinically indicated
13. Survival status update per [Section 7.5](#)
14. Update only newly diagnosed autoimmune disease.
15. Only treatments for prostate cancer should be captured during the LTFU Phase.
16. After the initial LTFU visit, all subsequent follow-up LTFU visits can be conducted by phone if the subject cannot visit the clinic.

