3.1.4 Exploratory Objectives

To model secondary radiological disease progression over the first year of study participation.

To ascertain whether a greater proportion of subjects randomized to either Arm V+G or Arm V remain event-free (radiological progression) six months post End-of-Treatment visit (using scans at End-of-Treatment visit as a new baseline), as compared to the subjects randomized to Arm P. This analysis will include all subjects, and separately the HLA-A2-expressing subgroup.

To assess the role of post-treatment anti-cancer therapies as an alternative explanation for observed survival differences.

To ascertain whether the survival of HLA-A2-expressing subjects randomized to Arm V+G, or Arm V is superior to that from HLA-A2-expressing-subjects randomized to Arm P.

To ascertain whether a greater proportion of HLA-A2 expressing subjects randomized to Arm V+G or to Arm V remain event-free at six months as compared to the HLA-A2 expressing subjects randomized to Arm P.

To compare arms with respect to immune response to immunizing antigen (PSA), as well as to non-vaccine containing prostate antigens, and tumor-associated antigens, and assess whether immune responses are prognostic and/or predictive.

To evaluate for baseline biomarkers which are prognostic and/or predictive of long term survival outcome.

To compare arms with respect to vaccine effects on circulating tumor cell (CTC) levels (US sites only).

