7.5 Assessments During Long-Term Follow-Up

The Long-Term Follow-Up (LTFU) phase begins immediately after the End-of-Treatment visit regardless of the total number of vaccinations actually received by a subject. The first visit is 6 calendar months \pm 14 days after the End-of-Treatment visit with consecutive visits every 6 months \pm 14 days thereafter. Subjects who progress prior to or during the LTFU phase will continue to be followed for survival and as described below until study closure or death.

First LTFU visit at 6 Months \pm 14 Days from the End-of-Treatment visit

- 1. Concomitant medications (limited to the treatment of prostate cancer therapy). All previously recorded medication entries should be reviewed for stop dates.
- 2. Prostate cancer treatment update for procedures, including interim unscheduled laboratory tests and/or radiological assessments.
- 3. Update for newly diagnosed autoimmune disease.
- 4. Physical exam (limited to assessment of subject's prostate cancer status including prostate cancer progression), vital signs, and weight.
- 5. QoL (FACT-P, BPI-SF and EQ-5D-3L)
- 6. Blood samples obtained for:
 - i. Serum for immune and biomarker status.
 - ii. Peripheral blood RNA/biomarker analysis
 - iii. CTC quantification (US sites only)
 - iv. PSA and PAP

v. Immune functional assays (US sites only)

7. CT* and bone scan

* For subjects with allergies to contrast agents, MRIs for abdomen and pelvis may be performed. Only in cases where MRI is unavailable may a non-contrast CT be performed. For subjects enrolled in [REDACTED], MRI must be used as the primary imaging modality.

Subsequent LTFU visits thereafter (every 6 Months ± 14 Days, phone call is acceptable)

1. Survival status
2. Any anti-prostate cancer therapy
3. Update for newly diagnosed autoimmune disease

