3.2.3. Exploratory Endpoint

The exploratory efficacy endpoint for the study is the proportion of subjects Alive Without Event (AWE) (radiographic progression, pain progression, chemotherapy initiation, or death) at the 6 month LTFU visit compared to placebo. For all subjects alive at the Week 25 (EOT) visit we will assess AWE at the 6 month LTFU visit. Subjects with pain progression or initiating

chemotherapy for prostate cancer at the Week 25 (EOT) visit will be counted as having an event at the 6 month LTFU visit.

Progression events at the 6 month LTFU visit will be defined as:

- Radiographic progression (per central radiology assessment) taking the Week 25 (EOT) visit scan as baseline
 - Two new lesions on bone scan, new metastases on CT scans*, or an increase size of nodal lesions per RECIST 1.1.
- Pain progression**
 - Introduction of scheduled opioid narcotics for cancer-related pain control. Scheduled opioid narcotics are defined as continuous daily use lasting more than 14 days.
- Initiation of chemotherapy for prostate cancer
- Death

* For subjects with allergies to contrast agents, MRIs for abdomen and pelvis may be performed. Only in cases where MRI is unavailable may a non-contrast CT be performed.

** The start date for an event of pain progression is defined as day 1 of first opioid regimen lasting more than 14 days.

This will attempt to define effects on secondary progression, and characterize delayed effects of investigational vaccine therapy.

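### The exploratory AWE endpoint at the 6-month LTFU visit counts new scheduled opioid use, but the protocol makes no provision to record opioids started after Week 25

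*Protocol*

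**What the plan says.** **Endpoint.** SAP 3.2.3 defines AWE at the 6-month LTFU visit as a composite of radiographic progression from the Week 25 scan, pain progression, chemotherapy for prostate cancer, and death. The pain event is "Introduction of scheduled opioid narcotics for cancer-related pain control. Scheduled opioid narcotics are defined as continuous daily use lasting more than 14 days". Its date is fixed as follows: "The start date for an event of pain progression is defined as day 1 of first opioid regimen lasting more than 14 days". Men with pain progression at Week 25 are carried forward as events, as are those initiating "chemotherapy for prostate cancer at the Week 25 (EOT) visit will be counted as having an event at the 6 month LTFU visit". The stated purpose is: "This will attempt to define effects on secondary progression, and characterize delayed effects of investigational vaccine therapy".

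**Data collection.** Protocol 7.5 lists, for the first LTFU visit, "Concomitant medications (limited to the treatment of prostate cancer therapy"), and asks that earlier entries be checked for stop dates. Footnote 15 of the schedule of events (Protocol 14.1), attached to concomitant medications at that visit, reads "Only treatments for prostate cancer should be captured during the LTFU Phase".

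**Protocol objective.** Protocol 3.1.4 is narrower than the SAP. It asks whether more men "remain event-free (radiological progression) six months post End-of-Treatment visit", with the End-of-Treatment (EOT) scans as the new baseline. Protocol 3.1.2.1 also describes the 12-month exploratory endpoint as radiological. SAP 4.4, on changes to the planned analysis, mentions tumor growth-rate analysis and interim analysis but not the move to a composite.

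**The concern.** The SAP asks for an event that the protocol does not tell sites to record. To classify a man on the pain component after Week 25, the analyst needs the drug, its indication, its start date and evidence of more than 14 days of daily use. The LTFU medication rule leaves out new analgesics. Pain progression present at Week 25 was recorded during treatment and is counted.

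What is at stake is interpretation. The endpoint exists to look for an effect that emerges late. If its pain component is filled mainly from the treatment period, an arm difference that arose before Week 25 can appear in a result labelled as delayed, and a true later difference in pain can go unrecorded.

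**Working it through.** The documents give no sample size, power or event rate for this endpoint, so there is no planned figure to reproduce. The check compares what the definition needs with what is collected.

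**1. Candidate sources for an opioid started after Week 25**

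| Source | What it gives | Enough for the SAP definition? |
|---|---|---|
| LTFU medications (Protocol 7.5; 14.1, footnote 15) | Prostate cancer treatment; stop dates for earlier entries | No: a new opioid is not called for |
| Adverse events (Protocol 8.12) | Reporting period ends 28 days after the last dose | No: see step 2 |
| BPI-SF item 7 at the first LTFU visit (Protocol 7.5, 14.8) | Pain treatment being received at the time | No: as printed, no start date, schedule or duration; SAP 10 only lists quality-of-life data |
| Examination at the first LTFU visit (Protocol 7.5) | Prostate cancer status, including progression | No: no opioid regimen is requested |
| Follow-up medications (SAP 7.1) | A listing of drugs started more than 28 days after the last dose | No: it can list only what sites entered |

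Scans, prostate cancer therapy (hence chemotherapy) and survival are collected in LTFU. Only the pain component lacks a source.

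**2. How far treatment-phase capture reaches past EOT**

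Take the last vaccine injection as day 0. The last GM-CSF or placebo injection is then day 3, and EOT is 28 ± 3 days, that is day 25 to 31 (Protocol 7.4).

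- 28 days from the last vaccine ends on day 28: at most 28 − 25 = 3 days past EOT.
- 28 days from the last GM-CSF or placebo ends on day 31: at most 31 − 25 = 6 days past EOT.

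Taking six months as about 182 days (an assumption), 6/182 = 3.3% of the interval at most, and 0% when EOT falls on day 31. No visit is scheduled after EOT within that window. A regimen already recorded at EOT can be shown to have exceeded 14 days once its stop date is entered, but its day 1 precedes the new baseline.

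**3. Three men followed through the rules as written**

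- Starts scheduled opioids two months after EOT, with no new lesion, no chemotherapy, and alive: coded event-free.
- Starts scheduled opioids after EOT and then chemotherapy before the LTFU visit: coded as an event, through chemotherapy.
- Already has pain progression at Week 25: coded as an event at the LTFU visit by carry-forward.

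Misclassification is thus confined to men whose only event after Week 25 is opioid initiation.

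**4. Size**

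Let q be the share of an arm's analysed subjects in that position. Recorded AWE = true AWE + q. The between-arm difference is distorted by q(experimental) − q(control). The documents give no value for q. For illustration only, q = 2%, 5% or 10% overstates that arm's AWE by 2, 5 or 10 percentage points. This restates the assumption; it is not an estimate.

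**The case against.** **The gap may be smaller in practice.** The eCRF is not among the documents, and a site could read footnote 15 as covering opioids for cancer pain. A reader might infer that the pain component can hold nothing but events from before the baseline. That is too absolute: the form may ask for more than the protocol, the reporting window can run up to 6 days past EOT, and BPI-SF may reveal opioid use. What stands is that none of these reliably gives the event as defined. Section 7.5 words the limit as prostate cancer therapy, which points away from analgesics, and if sites differ in their reading, ascertainment is uneven.

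**Chemotherapy will catch many of these men.** Protocol 1.3 says that most patients and physicians turn to chemotherapy once disease is symptomatic or accelerating. This stands and limits the number affected.

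**The SAP already admits the confounding.** SAP 8.5.2 says that the 12-month comparison is open to confounding by post-randomization events, and it models 12-month AWE with 6-month AWE as a covariate. This answers part of the carry-over concern in that model. SAP 8.4, the main analysis of this endpoint, has no such covariate, and adjustment cannot restore unrecorded events.

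**Carry-forward is defensible.** One might want to count only pain and chemotherapy events with onset after Week 25. Men already on opioids or chemotherapy at Week 25 would then be scored event-free or dropped after randomization. The objection stands, and the rule should stay.

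**It is only exploratory.** The endpoint has no allocated alpha, and delayed effect is handled mainly in the survival design. This limits the importance of the point but does not remove the mismatch.

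**Conclusion.** SAP 3.2.3 and the LTFU data collection in Protocol 7.5 and 14.1 do not fit together. Under the plan as written, pain events after the Week 25 baseline are not reliably captured, a man whose only event is a new scheduled opioid is coded alive without event, and pain progression or chemotherapy present at Week 25 is carried forward. The recorded pain component therefore mainly describes the period before the baseline.

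The size cannot be derived from the documents. A reader might apply the hypothesised hazard ratio of 0.68 to opioid initiation from Week 25 and compute a lost treatment difference. The documents do not support that: 0.68 is a survival hazard ratio, nothing ties it to opioid use, and under the planned delay it is reached only at 8 months.

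The conclusion assumes that sites follow the protocol text and that the eCRF does not collect opioids separately in LTFU. It covers the pain component of one exploratory endpoint. Overall survival, Week 25 AWE, and the scan, chemotherapy and death components are unaffected.

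**What to change.** 1. **Protocol 7.5 and 14.1, footnote 15.** Add opioid analgesics for cancer pain to what is recorded at the first LTFU visit: drug, scheduled or as needed, start and stop dates. For men already past that visit, collect the information retrospectively where possible.
2. **SAP 3.2.3 and 8.4.** Also report the protocol-defined endpoint, radiographic progression from the Week 25 scans, which the collected data fully support. Keep the composite and its carry-forward rule, but tabulate its events by component and by onset before or after Week 25. State that the pain component will not be interpreted as a delayed effect unless opioid data after Week 25 were captured.

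**Cost.** The second change is SAP wording and one table, with no new data. The first adds a medication category at an existing visit, with no new visit or test. It does need a protocol amendment with ethics approval before it takes effect at each site (Protocol 11.9), with 250 to 300 centers planned. SAP 4.1.5 and Appendix B show that accrual was under way when the SAP was revised, so ascertainment may be uneven for men already past the visit. If the amendment is judged not worthwhile, the second change alone still yields an interpretable endpoint.
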